## Pregnancy

While not an adverse event, pregnancy in a study subject must be reported to AbbVie within 24 hours after the site becomes aware of the pregnancy. Subjects who become pregnant during the study must be discontinued (Section 5.5).

All subjects should be informed of the contraceptive measure requirements. If a pregnancy occurs in a study subject or in the partner of a study subject, information regarding the pregnancy and the outcome will be collected.

In the event of pregnancy occurring in a subject's partner during the study, written informed consent for release of medical information from the partner must be obtained prior to collection of any pregnancy-specific information, and the pregnancy will be followed to outcome.

AbbVie will provide a separate consent form for this purpose. Pregnancy in a subject's partners will be collected from the date of the first dose through 30 days following the last dose of study drug or at least 90 days after the last dose of the selected combination.

The pregnancy outcome, for either mother or infant, of an elective or spontaneous abortion, stillbirth or congenital anomaly is considered a serious adverse event and must be reported to AbbVie within 24 hours after the site becomes aware of the event.

## 6.2 Toxicity Management

---

The management of specific adverse events and laboratory parameters is described below. This includes adverse events of TLS and neutropenia for venetoclax. Subjects will be monitored for these events throughout the study and treatment may be discontinued or adjusted as appropriate.

### Prophylaxis and Management of Tumor Lysis Syndrome

There is a potential risk for TLS in subjects with AML, especially in those with elevated leukocyte count, circulating blasts, elevated pretreatment LDH levels, dehydration, or renal dysfunction.

Venetoclax can cause rapid reduction in tumor and thus poses a risk for TLS. Changes in electrolytes consistent with TLS that require prompt management can occur as early as 6 to 8 hours following the first dose of treatment ([Appendix F](#)). Definitions of laboratory TLS and clinical TLS are provided in [Appendix E](#) (Howard grading classification). If a subject experiences blood chemistry changes suggestive of TLS, the dose of venetoclax may be withheld and/or reductions may be required.

Tumor lysis syndrome prophylaxis must be initiated in all subjects before the first dose of study drug or first new escalated dose. For subjects who had dose delay or interruptions TLS prophylactic measures may need to be implemented based on the disease status prior to resuming treatment. Below are the minimum requirements for TLS prophylaxis and management. Additional prophylaxis and monitoring procedures for TLS should be implemented as per institutional/regional standards.

- An oral agent to reduce the uric acid level (e.g., allopurinol) to be initiated at least 72 hours prior to dosing. Treatment may need to be continued for up to 28 days based on the ongoing risk of TLS development. Subjects allergic to or otherwise unable to receive allopurinol must use another uric acid reducer starting at least 72 hours prior to dosing or rasburicase on the day of treatment (prior to venetoclax dosing).
- Adequate hydration per day starting from at least 24 hours prior to first dose or any dose escalation.
- TLS Chemistry panel (creatinine, potassium, calcium, inorganic phosphorus, lactate dehydrogenase, and uric acid) will be performed real-time pre-dose, 4 - 6 hours post-dose and 24-hours post-dose for each venetoclax dose escalation, and as deemed necessary per investigator to monitor TLS.
- TLS Chemistry panel results (creatinine, potassium, calcium, inorganic phosphorus, lactate dehydrogenase, and uric acid) must be reviewed by the investigator in real time and prior to the subject's next dose to ensure appropriate subject management.
- If any clinically significant laboratory changes are observed within the first 24 hours after initiation of dosing or after a dose escalation, see [Appendix F](#) for management guidelines. Refer to table in [Appendix E](#) for definitions of laboratory and clinical TLS.
- If subjects develop TLS and the treatment is withheld, they should be admitted and managed as inpatient until the ramp-up is complete and TLS labs have normalized.

Subjects with reduced renal function ( $\text{CLcr} < 80 \text{ mL/min}$ , Cockcroft-Gault formula) require more intensive prophylaxis and monitoring to reduce the risk of TLS when initiating treatment with venetoclax. For subjects with a higher risk for TLS and lower creatinine clearance, additional measures with more intensive lab monitoring and intervention should be implemented ([Appendix F](#)).

If a subject meets criteria for clinically significant laboratory or clinical TLS please follow institutional guidelines or recommendations in [Appendix G](#); no additional venetoclax dose should be administered until resolution.

For continued dosing of venetoclax, monitor for evidence of TLS during study treatment, and manage abnormalities of serum creatinine, and electrolytes promptly. After resolution of electrolyte imbalances ([Appendix F](#)), venetoclax may be continued at the original dose after discussion between the investigator and the AbbVie TA MD.

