## APPENDIX E. DEFINITIONS OF LABORATORY AND CLINICAL TUMOR LYSIS SYNDROME

Metabolic Abnormality	Criteria for Classification of Laboratory Tumor Lysis Syndrome	Criteria for Classification of Clinical Tumor Lysis Syndrome
Hyperuricemia	Uric acid > 8.0 mg/dL (475.8 $\mu$ mol/L) in adults	
Hyperphosphatemia	Phosphorus > 4.5 mg/dL (1.5 mmol/L) in adults	
Hyperkalemia	Potassium > 6.0 mmol/L	Cardiac dysrhythmia or sudden death probably or definitely caused by hyperkalemia
Hypocalcemia	Corrected calcium < 7.0 mg/dL (1.75 mmol/L) or ionized calcium < 1.12 mg/dL (0.3 mmol/L) a	Cardiac dysrhythmia, sudden death, seizure, neuromuscular irritability (tetany, paresthesias, muscle twitching, carpopedal spasm, Trousseau's sign, Chvostek's sign, laryngospasm, or bronchospasm), hypotension, or heart failure probably or definitely caused by hypocalcemia
Acute kidney injury b	Not applicable	Increase in the serum creatinine level of 0.3 mg/dL (26.5 $\mu$ mol/L) (or a single value > 1.5 $\times$ the upper limit of the age-appropriate normal range if no baseline creatinine measurement is available) or the presence of oliguria, defined as an average urine output < 0.5 mL/kg/hr for 6 hrs

a. The corrected calcium level in mg/dL = measured calcium level in mg/dL + 0.8  $\times$  (4-albumin in g/dL).

b. Acute kidney injury is defined as an increase in the creatinine level of at least 0.3 mg/dL (26.5  $\mu$ mol/L) or a period of oliguria lasting 6 hours or more. By definition, if acute kidney injury is present, the subject has clinical tumor lysis syndrome.

Note: In laboratory tumor lysis syndrome, 2 or more metabolic abnormalities must be present during the same 24-hour period within 3 days before the start of therapy or up to 7 afterward. Clinical tumor lysis syndrome requires the presence of laboratory tumor lysis syndrome plus an increased creatinine level, seizures, cardiac dysrhythmia, or death.

Source: Howard SC, Jones DP, Pui CH. The tumor lysis syndrome. N Engl J Med. 2011;364(19):1844-54.

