**NOTES:**

- a. Assessments of ECOG Performance status, physical examination, vital signs, urine pregnancy test, clinical chemistry, hematology, coagulation, and measurement of weight are to be performed prior to first dose of study drug administration.
- b. If the screening physical examination is performed within 7 days of Cycle 1 Day 1, it is not required to repeat the exam on Cycle 1 Day 1 unless clinically indicated.
- c. A urine pregnancy test is to be performed prior to the first dose of study drug on Cycle 1 Day 1, if it has been > 7 days since obtaining screening serum pregnancy test results.
- d. Laboratory monitoring for TLS to occur at pre-dose, 4 - 6 hours post-dose, and 24 hours post-dose, for each venetoclax dose escalation.
- e. TLS Prophylaxis will be done according to the guidelines in the Protocol, Section 6.2, and as per institutional guidelines.
- f. Venetoclax will be administered orally in a 3-step ramp-up in 3 days to target dose of 400 mg/day: Day 1 – 100 mg, Day 2 – 200 mg, Day 3 – 400 mg, and then 400 mg daily thereafter. If on concomitant posaconazole, strong or moderate CYP3A inhibitors, or P-gp inhibitors, refer to the Protocol, Table 1, for dose modifications.
- g. Depending on Investigator's choice of azacitidine or decitabine at Cycle 1 Day 1 (as per institutional practice): Azacitidine (75 mg/m^2) subcutaneous (SC) or intravenous (IV) will be administered beginning at Cycle 1 Day 1 for 7 days of each 28-day cycle. Decitabine (20 mg/m^2) intravenous (IV) will be administered beginning at Cycle 1 Day 1 for 5 days of each 28-day cycle. The subject must remain on the assigned therapy for the duration of the study.
- h. On the days subject is given either azacitidine or decitabine, venetoclax must be dosed in the clinic and administered prior to these agents.

 INTERVIEW	
 
Adverse event assessment
 
Prior/concomitant therapy
 

 EXAM	
 
Vital signs
 

 LAB	
 
TLS risk assessment
 
Laboratory monitoring for TLSa
 

 TREATMENT	
 
Dosing with venetoclaxb,e
 
Dosing with azacitidine or decitabined,e
 
TLS Prophylaxisc
 

**NOTES:** Dose Day 4 is to occur 24 hours post-Day 3 dose.

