- Laboratory monitoring for TLS to occur at pre-dose, 4 - 6 hours post-dose, and 24 hours post-dose, for each venetoclax dose escalation.
- Venetoclax will be administered orally in a 3-step ramp-up in 3 days to target dose of 400 mg/day: Day 1 – 100 mg, Day 2 – 200 mg, Day 3 – 400 mg, and then 400 mg daily thereafter. If on concomitant posaconazole, strong or moderate CYP3A inhibitors, or P-gp inhibitors, refer to the Protocol, Table 1 for dose modifications.
- TLS Prophylaxis will be done according to the Protocol, Section 6.2, and as per institutional guidelines.
- Depending on Investigator's choice of azacitidine or decitabine at Cycle 1 Day 1 (as per institutional practice): Azacitidine (75 mg/m^2) SC or IV administered for 7 days beginning on Day 1 of each 28-day cycle. Decitabine (20 mg/m^2) IV administered for 5 days beginning on Day 1 of each 28-day cycle. The subject must remain on the assigned therapy for the duration of the study.
- On the days subject is given either azacitidine or decitabine, venetoclax must be dosed in the clinic and administered prior to these agents.

## CYCLE 1 DAYS 5 to 7

	INTERVIEW	
 
Adverse event assessment
 
Prior/concomitant therapy
 

	EXAM	
 
Vital signs
 

	LAB	
 
TLS risk assessmenta
 
Laboratory monitoring for TLSa
 

	TREATMENT	
 
Dosing with venetoclaxb
 
Dosing with azacitidine or decitabinec
 

**NOTES:** Administration Day 5 to 7 for subjects on azacitidine. Day 5 for subjects on decitabine (or dosed as per institutional practice).

- For subjects on dose modification per Protocol, Table 1, where ramp-up occurs over 4 days, TLS risk assessment and laboratory monitoring would be performed on Day 5 (24 hours post-venetoclax dose escalation).
- Venetoclax (400 mg) PO will be administered QD for each 28-day cycle except Cycle 1, due to 3-day ramp-up. If the subject is on concomitant posaconazole, strong or moderate CYP3A inhibitors, or P-gp inhibitors, refer to the Protocol, Table 1, for dose modifications. On the days the subject is given either azacitidine or decitabine, venetoclax must be dosed in the clinic and administered prior to these agents.

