**Table 1. Clinical Laboratory Tests**

Hematology	Clinical Chemistry a	Other Tests
Hematocrit	Blood urea nitrogen (BUN)	Urine and serum
Hemoglobin	Creatinine	- human chorionic gonadotropin c,d,e - Follicle-stimulating hormone c,d,f
Red blood cell (RBC) count	Calculated or measured creatinine clearance	
White blood cell count (WBC)	Total bilirubin	
Neutrophils	Albumin	TLS Chemistry Panela,g
Bands (if detected)	Alanine transaminase (SGPT/ALT)	Creatinine
Lymphocytes	Aspartate transaminase (SGOT/AST)	Potassium
Monocytes	Alkaline phosphatase	Calcium
Basophils (if detected)	Sodium	Inorganic phosphorus
Eosinophils (if detected)	Potassium	Lactate dehydrogenase
Platelet count (estimate not acceptable)	Calcium	Uric acid b
Blast count	Inorganic phosphorus	
	Uric acid b	Coagulation
	Total protein	Prothrombin time (PT)
	Glucose	Activated partial thromboplastin time (aPTT)
	Bicarbonate/CO 2	
	Chloride	
	Lactate dehydrogenase	

TLS = tumor lysis syndrome

- All chemistries should be performed at as specified in Section 2.1 and Section 2.2.
- At room temperature, rasburicase causes enzymatic degradation of the uric acid in blood/plasma/serum samples potentially resulting in spuriously low plasma uric acid assay readings. The following special sample handling procedure must be followed to avoid ex vivo uric acid degradation. Uric acid must be analyzed in plasma. Blood must be collected into prechilled tubes containing heparin anticoagulant. Immediately immerse plasma samples for uric acid measurement in an ice water bath. Plasma samples must be prepared by centrifugation in a precooled centrifuge (4°C). Finally, the plasma must be maintained in an ice water bath and analyzed for uric acid within 4 hours of collection.
- Performed only at Screening or Cycle 1 Day 1, as specified in the activity schedule and Section 2.1.
- Females only.
- Pregnancy testing is not required for females of non-childbearing potential.
- If needed to determine postmenopausal status.
- TLS chemistry samples for TLS monitoring will occur at pre-dose, 4 to 6 hours post-dose, and 24 hours post-dose for each venetoclax dose escalation.

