10.3.2 Statistical Methods

For each lab test for which NCI criteria exist, shift tables will be generated that cross tabulate the number of subjects with baseline values of Grade 0, Grade 1, Grade 2, Grade 3, or Grade 4 versus maximum post-baseline of Grade 0, Grade 1, Grade 2, Grade 3, or Grade 4. All treated subjects will be included in the cross tabulation regardless whether baseline or post-baseline measurements are collected.

Separate laboratory shifts tables based on the two criteria below will be generated for each laboratory tests related to CTCAE:

- Shifts from Grade 0 (Normal) at baseline to Grade 1 - 4 Post-baseline (maximum) and worsening from an abnormal baseline value of at least one grade up post-baseline (maximum)
- Shifts from Grade 0 - 2 at baseline to Grade 3 or 4 Post-baseline (maximum) and from Grade 3 at baseline value to Grade 4 post-baseline (maximum).

The maximum NCI grade value is the value with highest NCI grade collected after the first dose of study drug and within 30 days following the last dose of study drug. In cases where multiple values are collected on the same day, the maximum grade value and minimum grade value will be selected as the value for that day for the post-baseline grade value and for the baseline grade value, respectively.

Detailed listings of data for subjects experiencing NCI CTCAE Grade 3 to 4 blood chemistry and hematology values will be provided. All measurements collected, regardless of the number of days after the last dose of study drug, will be included in these listings.

The number and percentage of subjects with liver Enzyme value meeting the criteria for potential drug-induced liver injury ($ALT > 3 \times ULN$ or $AST > 3 \times ULN$ and $TBILI > 2 \times ULN$ within 72 hours [3 days if time stamp is not collected] of each other) will be presented.

The number and percentage of subjects meeting the Howard criteria for TLS will be presented. The Howard Criteria for TLS is defined as two or more of the following treatment-emergent lab changes within a 24-hour period. The evaluation period for TLS is after 1st dose of study drug to 7 days from the 1st dose of study drug.

- uric acid $> 475.8 \text{ mcmol/l}$,
- potassium $> 6 \text{ mmol/l}$,
- inorganic phosphorus $> 1.5 \text{ mmol/l}$
- calcium $< 1.75 \text{ mmol/l}$.

11.0 Summary of Changes Between the Previous Version of SAP and the Current SAP

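### The ramp-up TLS panel has no albumin or ionized calcium, so Appendix E's hypocalcaemia criterion can only be approximated after the first dose, and the SAP's TLS count uses a different calcium rule

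*Protocol*

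**What the plan says.** **Definition.** Protocol Appendix E gives the hypocalcaemia criterion for laboratory TLS as "Corrected calcium < 7.0 mg/dL (1.75 mmol/L) or ionized calcium < 1.12 mg/dL (0.3 mmol/L". Footnote a supplies the correction: "The corrected calcium level in mg/dL = measured calcium level in mg/dL + 0.8" × (4 − albumin in g/dL). Laboratory TLS needs at least two abnormalities within the same 24 hours.

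**What is measured.** Protocol Section 6.2 (Prophylaxis and Management of Tumor Lysis Syndrome) says: "TLS Chemistry panel (creatinine, potassium, calcium, inorganic phosphorus, lactate dehydrogenase, and uric acid) will be performed real-time pre-dose". Section 6.1 and Operations Manual Table 1 name the same six analytes. Table 1 lists albumin under general clinical chemistry only, and lists ionized calcium nowhere.

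**When.** Operations Manual Table 1 says that "TLS chemistry samples for TLS monitoring will occur at pre-dose, 4 to 6 hours post-dose, and 24 hours post-dose for each venetoclax dose escalation". On Cycle 1 Day 1, "clinical chemistry, hematology, coagulation, and measurement of weight are to be performed prior to first dose of study drug administration", so one albumin result is available before treatment. The visit lists for Cycle 1 Days 2–4 and 5–7 contain TLS monitoring but no general chemistry. General chemistry returns on Day 28. A Day 5 TLS draw applies only "where ramp-up occurs over 4 days, TLS risk assessment and laboratory monitoring would be performed on Day 5".

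**What is analysed.** SAP Section 10.3.2 reports the number and percentage of subjects meeting the Howard criteria in the 7 days after first dose. Its calcium component is calcium below 1.75 mmol/L, with no albumin correction and no ionized alternative.

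**The concern.** The protocol defines one quantity, the ramp-up schedule collects the inputs for another, and the SAP analyses that other one under the same name. Section 6.2 has the investigator review each panel before the next dose and points to Appendix E for the definition of TLS, so the corrected value is wanted in real time as well as at analysis.

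The rate of TLS is named in the secondary objective on adverse events (Protocol Section 3.1, SAP Section 4.1), and safe outpatient initiation is the reason for the study. With about 60 subjects, one reclassified subject moves a reported percentage by 1/60 = 1.7 points.

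Rewording the SAP alone would not close the gap, because the albumin that belongs to each sample is not required. Adding albumin alone would not change the reported Howard count either, because the SAP does not use it. The two changes have to go together.

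**Working it through.** **1. The plan's own figure.** Appendix E equates 7.0 mg/dL with 1.75 mmol/L. With a molar mass of 40.078 g/mol for calcium, 7.0 × 10 / 40.078 = 1.747, which rounds to 1.75. The Appendix E and SAP limits are therefore numerically the same. The difference lies in which calcium is compared with them.

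**2. Draws without a same-sample albumin.** Each escalation needs a pre-dose, a 4–6 hour and a 24 hour sample. I treat each 24 hour sample as the next day's pre-dose sample.

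- 3-step ramp-up: 3 × 2 + 1 = 7 draws.
- 4-step ramp-up (strong CYP3A inhibitor or posaconazole, Protocol Table 1): 4 × 2 + 1 = 9 draws.
- Scheduled general chemistry coincides only with the Day 1 pre-dose draw. Without albumin: 7 − 1 = 6 of 7, or 9 − 1 = 8 of 9. These are all the draws after the first dose, including the Day 1 sample at 4–6 hours.

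**3. Distance between the two calcium rules.** Solving footnote a for measured calcium, corrected calcium is below 7.0 mg/dL when measured calcium is below 7.0 − 0.8 × (4 − albumin). The documents give no albumin values, so the range below is assumed.

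| Albumin (g/dL) | Appendix E cut on measured calcium (mg/dL) | SAP cut (mg/dL) | SAP minus Appendix E |
|---|---|---|---|
| 2.5 | 5.8 | 7.0 | +1.2 |
| 3.0 | 6.2 | 7.0 | +0.8 |
| 3.5 | 6.6 | 7.0 | +0.4 |
| 4.0 | 7.0 | 7.0 | 0 |
| 5.0 | 7.8 | 7.0 | −0.8 |

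In mmol/L, the 0.4–1.2 mg/dL difference is 0.10–0.30. For example, a measured 6.9 mg/dL corrects to 6.9 + 0.8 × 1.5 = 8.1 at albumin 2.5 g/dL and does not meet Appendix E. At albumin 4.0 g/dL it stays 6.9 and does. The SAP scores both as hypocalcaemia. Below 4 g/dL the SAP rule over-calls; above 4 g/dL it under-calls.

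**4. When this changes a subject's classification.** Four laboratory components are scored and two are needed. If none of the other three is abnormal, calcium alone is not enough. If two or more are abnormal in the same 24 hours, TLS is already met. Calcium decides only when exactly one other component is abnormal.

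**5. Error from carrying the Day 1 albumin forward.** By footnote a, each 1 g/dL change in albumin after Day 1 misstates corrected calcium by 0.8 mg/dL (0.20 mmol/L). A fall of 0.5 g/dL understates it by 0.4 mg/dL, so a residual over-call is possible.

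**The case against.** **The criterion is not wholly out of reach.** A reader might infer that it cannot be evaluated at all during ramp-up. The documents do not support that. Footnote a does not ask for albumin from the same sample, and a Day 1 value exists. Total calcium at or above 7.0 mg/dL also rules the criterion out whenever albumin is 4 g/dL or lower. What is missing is exact evaluation, chiefly confirmation of low values.

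**Sites may measure more.** Section 6.2 presents the panel as a minimum, leaves additions to institutional or regional standards, and allows further testing at the investigator's discretion. Section 6.1 introduces its list as non-exhaustive. Appendix F asks for corrected calcium, and for ionized calcium if albumin is low. But that line sits only in the row for symptomatic subjects with calcium at or below 7.0 mg/dL and presumes a known albumin. Nothing requires albumin at each draw, so collection may differ across about 20 sites using local laboratories.

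**True cases being missed.** A reader might infer this, but it would need calcium to go unscored, or albumin above 4 g/dL. The SAP does score calcium, and within 2.5–3.5 g/dL the uncorrected rule errs only towards calling too many.

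**Dosing.** A reader might also infer that every laboratory TLS finding forces venetoclax to be withheld. Section 6.2 ties its no-further-dose statement to clinically significant laboratory or clinical TLS and elsewhere says that the dose may be withheld. The Appendix F calcium row is triggered by calcium plus symptoms. Real-time management does not rest on corrected calcium alone.

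**The TLS rate has another source.** SAP Section 10.2.3 counts TLS adverse events by a MedDRA search that needs no calcium formula, and the SAP's Howard count can be computed from the panel as written. Both are true. But the Howard count then answers a different question from Appendix E, under a label that suggests the same one.

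**Conclusion.** The mismatch is real and limited. Every required ramp-up draw after the first dose (6 of 7, or 8 of 9) lacks the albumin or ionized calcium that Appendix E calls for, and the SAP's Howard count uses a calcium rule that agrees with Appendix E only at an albumin of 4 g/dL. The shift is 0.4–1.2 mg/dL at an assumed albumin of 2.5–3.5 g/dL.

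It matters only for subjects in whom calcium would be the deciding second abnormality. The documents give neither albumin values nor a laboratory-TLS rate, so the number reclassified cannot be estimated. Protocol Section 4.2 cites a program-wide clinical TLS rate below 1%, fewer than 60 × 0.01 = 0.6 expected clinical cases, but that does not bound the laboratory count. The primary endpoint is unaffected. The correction is worth making because it is cheap and lets the stated criterion be computed in the same way at every site.

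**What to change.** 1. Add albumin to the TLS chemistry panel in Protocol Sections 6.1 and 6.2 and Operations Manual Table 1, run on the sample already drawn.
2. Reconcile SAP Section 10.3.2 with Appendix E, so that the Howard count uses corrected calcium by footnote a, or ionized calcium where it was measured.
3. For subjects already treated, state in the SAP that corrected calcium uses the Cycle 1 Day 1 albumin, label it an approximation, and give its error (0.8 mg/dL per 1 g/dL change in albumin).
4. Report the count on uncorrected calcium as a sensitivity analysis, so that the effect of the correction is visible.

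The cost is one extra analyte per draw at the local laboratory and a few lines of SAP text. No visit or blood draw is added, and no dose or management rule changes.
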